6.1.5. Analysis Populations

The following major analysis populations will be used (additional analysis populations for specific analysis will be defined in the corresponding analysis section):

Intent-to-Treat Population (ITT Population): Unless otherwise specified, efficacy and health outcomes analyses for Period 2 will be conducted on the ITT Population, defined as all randomized patients, even if the patient does not take the assigned treatment, does not receive the

correct treatment, or otherwise does not follow the protocol. Patients will be analyzed according to the treatment to which they were assigned.

Per-Protocol Set (PPS): In addition, the primary efficacy analysis will be repeated using the PPS, which is defined as all randomized patients who are compliant with therapy, who do not have a subset of important protocol deviations that impact the primary efficacy endpoint (Section 6.15), and whose investigator site does not have significant good clinical practice (GCP) issues that require a report to the regulatory agencies prior to Week 16 (Visit 8). Compliance with therapy is defined to be missing no more than 20% of expected doses, not missing 2 consecutive doses (all injections at an injection week are counted as 1 dose), and not have any occurrence of over-dosing (that is, took more injections at the same time point than specified in the protocol) during Period 2.

Patients will be analyzed according to the treatment to which they were assigned.

Safety Population: Safety analyses for Period 2 will be conducted on the Safety Population, defined as all randomized patients who received at least 1 dose of study treatment. Patients will be analyzed according to the treatment to which they were assigned in that period.

Extended Treatment Period Population: Efficacy, health outcomes, and safety analyses for Period 3 will be conducted on the Extended Treatment Period Population, defined as all patients who received at least 1 dose of ixekizumab treatment during Period 3.

Adalimumab Washout Population: Treatment-emergent adverse event analyses for Period 3 from Week 16 to Week 20 will be conducted on the Adalimumab Washout Population, defined as all patients who were randomized to adalimumab at Week 0 and took at least 1 placebo dose from Week 16 through Week 20.

All Ixekizumab Exposures Safety Population: Safety analyses for combined Blinded Treatment Dosing Period and Extended Treatment Period will be conducted on the All Ixekizumab Exposures Safety Population, defined as all patients who received at least one dose of ixekizumab during the study. For each patient, only periods in which ixekizumab is administered are included.

Follow-Up Population: Safety analyses for Period 4 will be conducted on the Follow-Up Population, defined as all randomized patients who received at least 1 dose of study treatment and have entered the Period 4. Patients will be analyzed according to the treatment they received before entering the Follow-up Period.

[Table RHBV.6.1](#) summarizes the major analysis purposes intended for each analysis population.

[Table RHBV.6.2](#) describes the treatment groups and the comparisons for each study period and analysis population.

Table RHBV.6.1. Major Analysis Purposes Intended for Each Analysis Population

	ITT Population	Per-Protocol Set	Safety Population	Extended Treatment Period Population	Adalimumab Washout Population	ITT (Safety) Population Who are Initially Randomized to Ixekizumab at Week 0	All Ixekizumab Exposures Safety Population	Follow-Up Population
Disposition	For Period 2			For Period 3				For Period 4
Baseline Characteristics ^a	For baseline			For baseline				
Treatment Compliance			For Period 2	For Period 3				
Concomitant Medication	For Period 2			For Period 3				
Protocol Deviation	For Period 2			For Period 3				
Exposure			For Period 2	For Period 3		For Combined Periods 2 and 3	For Periods 2 and 3, on ixekizumab treatment only	
Efficacy and Health Outcome Analyses	For Period 2. For Period 4, ASAS40 only	For ASAS40, ASAS20 in Period 2		For Period 3		For primary and major secondary objectives, and selective measures in Combined Periods 2 and 3		
Safety Analyses			For Period 2	For Period 3	TEAE for Week 16 to Week 20	For Combined Periods 2 and 3	For Periods 2 and 3, on ixekizumab treatment only	For Period 4
Subgroup Analyses on Efficacy	For Period 2							
Subgroup Analyses on Safety Outcome			For Period 2					

Abbreviations: ASAS = Assessment of Spondyloarthritis International Society; ITT = intent-to-treat; TEAE = treatment-emergent adverse event.

^a including patient demographics and other baseline characteristics, historical illness, preexisting conditions, prespecified medical history, previous therapy.

Table RHBV.6.2. Treatment Groups and Comparisons for Each Study Period and Analysis Population

Study Period	Analysis Population	Treatment Group	Abbreviation	Comparison
Blinded Treatment Dosing Period (Period 2)	Intent-to-Treat Population;	Placebo Adalimumab 40 mg Q2W Ixezumab 80 mg Q4W Ixezumab 80 mg Q2W	PBO ADA40Q2W IXE80Q4W IXE80Q2W	ADA40Q2W vs. PBO IXE80Q4W vs. PBO
	Per Protocol Set;	Total Ixezumab Total	Total IXE Total	IXE80Q2W vs. PBO
	Safety Population	Add the following treatment groups for analyses evaluating the impact of ixekizumab starting dose: Ixezumab 80 mg Q4W / 80 mg Starting Dose Ixezumab 80 mg Q4W / 160 mg Starting Dose Ixezumab 80 mg Q2W / 80 mg Starting Dose Ixezumab 80 mg Q2W / 160 mg Starting Dose Total Ixezumab / 80 mg Starting Dose Total Ixezumab / 160 mg Starting Dose	IXE80Q4W/80S ^b IXE80Q4W/160S ^b IXE80Q2W/80S ^b IXE80Q2W/160S ^b Total IXE/80S ^b Total IXE/160S ^b	Overall ^a IXE80Q4W/80S ^b vs. IXE80Q4W/160S ^b ; IXE80Q2W/80S ^b vs. IXE80Q2W/160S ^b ; Total IXE/80S ^b vs. Total IXE/160S ^b
Extended Treatment Period (Period 3)	Extended Treatment Period Population	Placebo/Ixezumab 80 mg Q4W Placebo/Ixezumab 80 mg Q2W Adalimumab 40Q2W / Ixezumab 80 mg Q4W Adalimumab 40Q2W / Ixezumab 80 mg Q2W Ixezumab 80 mg Q4W / Ixezumab 80 mg Q4W Ixezumab 80 mg Q2W / Ixezumab 80 mg Q2W Placebo/Ixezumab 80 mg Adalimumab 40Q2W /Ixezumab 80 mg Ixezumab 80 mg / Ixezumab 80 mg Total Ixezumab 80 mg Q4W ^c Total Ixezumab 80 mg Q2W ^c Total	PBO/IXE80Q4W PBO/IXE80Q2W ADA40Q2W/IXE80Q4W ADA40Q2W/IXE80Q2W IXE80Q4W/IXE80Q4W IXE80Q2W/IXE80Q2W PBO/IXE ADA40Q2W/IXE IXE/IXE Total IXE80Q4W Total IXE80Q2W Total	No Between-Group or Overall Comparisons
Extended Treatment Period	Adalimumab Washout Population	Adalimumab 40 mg Q2W	ADA40Q2W	NA

Study Period	Analysis Population	Treatment Group	Abbreviation	Comparison
(Period 3)				
Combined Periods 2 and 3	Intent-to-Treat Population Who are Initially Randomized to Ixekizumab	Ixekizumab 80 mg Q4W Ixekizumab 80 mg Q2W Total Ixekizumab	IXE80Q4W IXE80Q2W Total IXE	No Between-Group or Overall Comparisons
Combined Periods 2 and 3	Safety Population Who are Initially Randomized to Ixekizumab	Ixekizumab 80 mg Q4W Ixekizumab 80 mg Q2W Total Ixekizumab	IXE80Q4W IXE80Q2W Total IXE	No Between-Group or Overall Comparisons
Combined Periods 2 and 3 (on Ixekizumab treatment only)	All Ixekizumab Exposures Safety Population ^e	Ixekizumab 80 mg Q4W Ixekizumab 80 mg Q2W Total Ixekizumab	IXE80Q4W IXE80Q2W Total IXE	No Between-Group or Overall Comparisons
Post-Treatment Follow-up Period (Period 4) ^d	Follow-Up Population	Placebo Adalimumab 40 mg Q2W Ixekizumab 80 mg Q4W Ixekizumab 80 mg Q2W Total Ixekizumab Total	PBO ADA40Q2W IXE80Q4W IXE80Q2W Total IXE Total	No Between-Group or Overall Comparisons

Abbreviations: ADA = adalimumab; IXE80Q2W = ixekizumab 80 mg every 2 weeks; IXE80Q4W = ixekizumab 80 mg every 4 weeks PBO = placebo; Q2W = every 2 weeks; Q4W = every 4 weeks.

- a Overall comparison will be conducted for demographics, historical illness, medical history, preexisting condition, and previous therapy. The between-group comparisons and the overall comparison will be conducted for concomitant therapy, compliance, disposition, and safety.
- b S = starting dose; differences between starting dose groups and 95% CI will be provided.
- c For Extended Treatment Period Population, ‘Total Ixekizumab 80 mg Q4W’ is a pooled group of ‘Placebo/Ixekizumab 80 mg Q4W’, ‘Adalimumab 40Q2W/Ixekizumab 80 mg Q4W’ and ‘Ixekizumab 80 mg Q4W/Ixekizumab 80 mg Q4W’; similarly, ‘Total Ixekizumab 80 mg Q2W’ is a pooled group of ‘Placebo/Ixekizumab 80 mg Q2W’, ‘Adalimumab 40Q2W /Ixekizumab 80 mg Q2W’ and ‘Ixekizumab 80 mg Q2W/Ixekizumab 80 mg Q2W’.
- d Treatment group refers to the treatment regimen that the patient received prior to entering Period 4.
- e defined as all patients who received at least one dose of ixekizumab during the study

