**Table RHBV.3. Treatment Regimens from Week 16 to Week 50**

Initial Regimen		Dose Week 16 a	Dose Week 18 to Week 50 (Period 3)
	Total injections per patients	2 injections	1 injection Q2W
ixekizumab 80 mg Q2W	Treatment dose	1 ixekizumab 80 mg injection	1 ixekizumab 80 mg injection Q2W (Beginning at Week 18, Q2W)
	Injections to maintain blinding	1 placebo for ixekizumab injection	None
ixekizumab 80 mg Q4W	Treatment dose	1 ixekizumab 80 mg injection	1 ixekizumab 80 mg injection Q4W (Beginning at Week 20, Q4W)
	Injections to maintain blinding	1 placebo for ixekizumab injection	1 placebo for ixekizumab injection Q4W (Beginning at Week 18, Q4W)
adalimumab 40 mg Q2W (comparator)		rerandomized to ixekizumab 80 mg Q2W or ixekizumab 80 mg Q4W b	
	Treatment dose	None	ixekizumab 80 mg Q2W or ixekizumab 80 mg Q4W beginning at Week 20
	Injections to maintain blinding	2 placebo for ixekizumab injections	1 placebo injection at Week 18 only (ixekizumab 80 mg Q2W regimen) or 1 placebo for ixekizumab injection Q4W beginning at Week 18 (ixekizumab 80 mg Q4W regimen)
placebo		rerandomized to ixekizumab 80 mg Q2W or ixekizumab 80 mg Q4W	
	Treatment dose	2 ixekizumab 80 mg injections (starting dose)	ixekizumab 80 mg Q2W beginning at Week 18 or ixekizumab 80 mg Q4W beginning at Week 20
	Injections to maintain blinding	None	None (ixekizumab 80 mg Q2W regimen) or 1 placebo for ixekizumab injection Q4W beginning at Week 18 (ixekizumab 80 mg Q4W regimen)

a Patients on placebo will receive a starting dose of 160 mg ixekizumab (2 ixekizumab 80 mg injections) at Week 16. All other patients will receive placebo injections as needed to maintain blinding.

b Patients assigned to the adalimumab treatment group at Week 0 will be re-randomized to an ixekizumab regimen at Week 16, but they will not receive an ixekizumab injection at Week 16. These patients will receive 2 placebo for ixekizumab injections at Week 16 to maintain the blind. Patients will receive their first ixekizumab dose (a single 80 mg injection) at Week 20, after the wash out period is complete. Patients will then maintain the ixekizumab regimen they were re-randomized to (ixekizumab 80 mg Q2W or ixekizumab 80 mg Q4W), with placebo injections as needed to maintain blinding.

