5.3. Determination of Sample Size

Approximately 320 patients will be randomized at a 1:1:1:1 ratio in the Blinded Treatment Dosing Period (Period 2) to ixekizumab 80 mg Q2W, ixekizumab 80 mg Q4W, adalimumab 40 mg Q2W, and placebo. With 80 patients per treatment group, this study will have approximately 96% power to test the superiority of ixekizumab Q2W to placebo for the ASAS40 at Week 16. The following assumptions were used for the power calculations for ASAS40 response rates at Week 16 regardless of starting dose: 44% for ixekizumab 80 mg Q2W treatment group and 16% for the placebo group. A 2-sided Fisher's exact test at the 0.05 level is assumed. These assumptions are based on the review of historical clinical studies in rad-axSpA (etanercept, adalimumab, infliximab, certolizumab, and golimumab [Davis et al. 2003; van der Heijde et al. 2005 and 2006; Inman et al. 2008; Landewé et al. 2014]) and recent secukinumab data in patients who are TNF-naïve (Baeten et al. 2014; Sieper et al. 2014).

6. A Priori Statistical Methods

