6.1.2. General Considerations for Analyses during the Extended Treatment Period (Period 3)

Unless otherwise specified, Period 3 starts at the first injection of study treatment at Week 16 (Visit 8) and ends on the date of Week 52 (Visit 15) or the ETV (between Weeks 16 and 52).

For the efficacy and health outcome analyses, baseline is defined as the last available value before the first injection in Period 2 and, in most cases, will be the value recorded at Week 0 (Visit 2).

Unless otherwise specified, for the safety analyses during Period 3, baseline is defined as the last available value before first injection of ixekizumab in Period 3. In most cases, this will be the measure recorded at Week 16 (Visit 8). For adalimumab patients in Period 2 who are randomized to ixekizumab during Period 3, this will be the measure recorded at Week 20 (Visit 9). For treatment-emergent adverse events (TEAEs), baseline is the events ongoing just prior to the first injection of the study drug injection at Week 16 (for placebo and ixekizumab patients) or Week 20 (for adalimumab patients who are randomized to ixekizumab during Period 3).

The number and percentage of patients having categorical efficacy response (for example, ASAS40) will be summarized by treatment group for all scheduled visits (NRI), including Week 52 (Visit 15) during Period 3.

In addition, the number and percentage of patients achieving response on ASAS20 for those who did not achieve response at Week 16, and the number and percentage of patients maintaining response for those who achieved response at Week 16, will be summarized by treatment group for all scheduled visits (NRI), including Week 52 (Visit 15) during Period 3. Similar summary will be provided for ASAS40.

Each continuous efficacy and health outcome score and change from baseline (or percent improvement) will be summarized by treatment group at all scheduled visits, including Week 52 (Visit 15) using descriptive statistics (n, mean, SD, median, minimum and maximum). Missing data will be imputed using mBOCF method (Section 6.3.2).

The categorical safety measures will be summarized with incidence rates. The mean change of the continuous safety measures will be summarized at all scheduled visits.

6.1.3. General Considerations for Analyses during Combined Blinded Treatment Dosing Period and Extended Treatment Period (Combined Periods 2 and 3)

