NSAID (including COX-2 inhibitors) Intake	Proportion of patients taking NSAID (including COX-2 inhibitors)	Descriptive statistics	Extended Treatment Period Population	At Baseline (Week 0), Weeks 16, 20, 24, 28, 32, 36, 44, 52.	Analyses on NSAID intake (Section 6.10.4.1)
	Change from baseline in ASAS-NSAID	Descriptive statistics	Extended Treatment Period Population who have NSAID (including COX-2 inhibitor) intake at baseline	At Weeks 16, 20, 24, 28, 32, 36, 44, 52.	Analyses on NSAID intake (Section 6.10.4.1)

Measure	Variable	Analysis Method (Sections 6.1, 6.3)	Population (Section 6.1.5)	Comparison/Time Point	Analysis Type
	ASAS-NSAID50; ASAS-NSAID10; ASAS-NSAID0	Descriptive statistics	Extended Treatment Period Population who have NSAID (including COX-2 inhibitor) intake at baseline	At Weeks 16, 20, 24, 28, 32, 36, 44, 52.	Analyses on NSAID intake (Section 6.10.4.1)

Abbreviations: ANCOVA = analysis of covariance; ASAS = Assessment of Spondyloarthritis International Society; ASDAS = Ankylosing Spondylitis Disease Activity Score; ASSpiMRI-Berlin = Ankylosing Spondylitis Spinal Magnetic Resonance Imaging-activity-Berlin Score; BASDAI = Bath Ankylosing Spondylitis Disease Activity Index; BASFI = Bath Ankylosing Spondylitis Functional Index; BASMI = Bath Ankylosing Spondylitis Metrology Index; CRP = C-reactive protein; ITT = intent-to-treat; IXE80Q2W = ixekizumab 80 mg every 2 weeks; IXE80Q4W = ixekizumab 80 mg every 4 weeks; KM = Kaplan-Meier; LOCF = last observation carried forward; MASES = Maastricht Ankylosing Spondylitis Enthesitis Score; mBOCF = modified baseline observation carried forward; MMRM = mixed-effects model of repeated measures; NRI = nonresponder imputation; NSAID = nonsteroidal anti-inflammatory drug; pMI = placebo multiple imputation; SJC = swollen joint count; SPARCC SIJ = Spondyloarthritis Research Consortium of Canada Score Sacroiliac Joint; TJC = tender joint count.

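### The pooled Total Ixekizumab columns for Period 3 efficacy include adalimumab switchers at Week 20, before they have had any ixekizumab (minor)

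*SAP*

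**What the plan says.** - **Pooled groups.** SAP Table RHBV.6.2 lists Total IXE80Q4W, Total IXE80Q2W and Total for the Extended Treatment Period Population. Footnote c gives their make-up ("Total Ixekizumab 80 mg Q4W’ is a pooled group of ‘Placebo/Ixekizumab 80 mg Q4W’, ‘Adalimumab 40Q2W/Ixekizumab 80 mg Q4W", plus the continuing ixekizumab group). It sets no restriction by type of table or by visit.
- **Use for efficacy.** SAP Table RHBV.6.1 assigns Period 3 efficacy and health outcomes to this population. Under Section 6.1.2, categorical responses "will be summarized by treatment group for all scheduled visits (NRI), including Week 52 (Visit 15) during Period 3". The same section adds ASAS20 and ASAS40 summaries split by Week 16 response status: later response in nonresponders, and response kept by responders.
- **Timing of exposure.** Protocol Table RHBV.3, footnote b, says of adalimumab switchers: "Patients will receive their first ixekizumab dose (a single 80 mg injection) at Week 20, after the wash out period is complete". They receive only placebo injections at Weeks 16 and 18. Placebo switchers receive ixekizumab at Week 16.
- **NSAID tables.** SAP Table RHBV.6.5 reports the ASAS-NSAID rows "At Weeks 16, 20, 24, 28, 32, 36, 44, 52" in the same population. Section 6.10.4.1 sets the look-back from the previous visit to the current one.
- **Safety and immunogenicity.** The SAP does deal with the gap here. It uses a Week 20 baseline for adalimumab switchers (6.1.2 and Table RHBV.6.10), an Adalimumab Washout Population, and an All Ixekizumab Exposures Safety Population that counts only time on ixekizumab (6.1.5). No matching rule exists for efficacy.

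**The concern.** A column headed as an ixekizumab regimen should describe patients who have had that regimen. Read as written, the Week 20 column does not. Patient Global, spinal pain, BASFI, BASDAI and CRP are all collected at Week 20 (Protocol Appendix 2), the visit at which adalimumab switchers take their first ixekizumab injection. The protocol does not fix the order of efficacy scales and dosing at that visit, but this hardly matters: Patient Global and spinal pain ask about the past week (Protocol 8.1.2.2 and 8.1.2.3), so the answers describe the washout.

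The summaries by Week 16 response status have a related fault that lasts to Week 52. In a pooled column, the patients whose response is being followed include some who achieved it on placebo or adalimumab. An adalimumab responder who loses response during washout would then appear under an ixekizumab heading as a response not maintained. Maintenance of the ixekizumab effect through Week 52 is a stated secondary objective.

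**Working it through.** **1. The plan's own figure, to confirm the arm sizes (SAP 5.3).** Inputs: "Approximately 320 patients will be randomized at a 1:1:1:1 ratio in the Blinded Treatment Dosing Period (Period 2"; "With 80 patients per treatment group, this study will have approximately 96% power to test the superiority of ixekizumab Q2W to placebo"; "44% for ixekizumab 80 mg Q2W treatment group and 16% for the placebo group"; 2-sided Fisher "exact test at the 0.05 level is assumed". Power is the sum over i, j = 0 to 80 of Bin(i; 80, 0.44) × Bin(j; 80, 0.16), counting the pairs with Fisher p ≤ 0.05. The result is 0.967, against the stated 96%. The figure of 80 per arm reproduces.

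**2. Size of the pooled columns.** Placebo patients are re-randomised 1:1 (Protocol 6.1), giving 40 per regimen. No ratio is stated for adalimumab patients; 1:1 is assumed here, also giving 40. Per regimen: 80 + 40 + 40 = 160. Overall Total: 320.

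**3. Share not yet exposed at Week 20.**
- Overall Total: 80/320 = 25%, whatever the adalimumab ratio.
- Each regimen column at 1:1: 40/160 = 25%.
- One regimen column at 1:2 or 2:1: 26.7/146.7 = 18.2%, or 53.3/173.3 = 30.8%.
- With assumed retention of 85% to 100% in adalimumab switchers and 90% to 100% in the others, at 1:1: from 34/(34 + 120) = 22% to 40/(40 + 108) = 27%.

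**4. Effect on the pooled Week 20 ASAS40 rate.** Let exposed patients respond at 44%, the plan's Q2W figure, used here for illustration. Let the not-yet-exposed respond at r, assumed between 16% and 44%. The pooled rate is 0.75 × 0.44 + 0.25 × r:

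| r | Pooled rate | Shift from 44% |
|---|---|---|
| 16% | 37% | 7 points |
| 30% | 40.5% | 3.5 points |
| 44% | 44% | 0 |

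**5. Pooled summaries of Week 16 responders.** Per regimen column, expected Week 16 responders are 80 × 0.44 = 35.2 on ixekizumab, 40 × 0.16 = 6.4 on placebo, and between 40 × 0.16 = 6.4 and 40 × 0.44 = 17.6 on adalimumab (rate assumed). Those who responded on something other than ixekizumab make up (6.4 + 6.4)/48.0 = 27% to (6.4 + 17.6)/59.2 = 41% of the denominator.

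**6. NSAID tables at Week 16.** The look-back ends at that visit, so neither switch group has been exposed: (40 + 40)/160 = 50% of each regimen column, and 160/320 = 50% of Total. Half of that share is placebo switchers and half is adalimumab switchers.

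**7. From Week 24** every group has had ixekizumab, and the unexposed share is 0.

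**The case against.** Several points on the other side stand.

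- Table RHBV.6.2 already lists all six switch sequences, together with PBO/IXE, ADA40Q2W/IXE and IXE/IXE, so a reader can see the unmixed groups.
- The Combined Periods 2 and 3 analysis (SAP 6.1.3) covers the primary and all major secondary endpoints in patients randomised to ixekizumab at Week 0, with no switchers.
- Period 3 has no between-group comparisons.
- The Week 16 NSAID share has little practical effect. Protocol Section 6.8 bars new NSAIDs and NSAID dose changes in Period 2 except for safety, so Week 16 intake is close to a reference value in every arm.
- The output shells are not in the documents. That the pooled columns appear in efficacy tables is inferred from the lack of any restriction.

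A reader might also infer more than the text supports:

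- **An artificial dip and rise over Weeks 16, 20 and 24.** The unexposed share only falls (50%, 25%, 0%). Period 3's first scheduled efficacy visit is Week 20, so its ASAS40 summary has no Week 16 point to dip from. Residual adalimumab effect at Week 20 is not given.
- **A pooled rate as low as 30%.** This requires lowering the placebo switchers as well: (80 × 0.44 + 80 × 0.16)/160 = 30%. By Week 20 they have had a 160 mg starting dose, so a low rate in them would reflect short exposure, not absence of exposure.
- **Patients never given ixekizumab.** The population requires at least one ixekizumab dose in Period 3. These patients are not yet dosed.
- **A fault in pooling by study week after Week 24.** Exposure durations differ, but the sequence columns show this and the practice is ordinary.

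These points limit the weight of the concern. They do not remove it: separate columns do not correct a pooled column whose heading is wrong.

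**Conclusion.** The point holds as a minor one. As written, the pooled efficacy columns at Week 20 count patients with no ixekizumab exposure. The 25% share of the overall Total rests on planned sizes and equal retention. The 25% share of each regimen column also needs the unstated 1:1 adalimumab ratio. Non-exposure alone would move the pooled ASAS40 rate by 0 to 7 points under the assumed response range; the documents do not allow a closer figure. The pooled summaries by Week 16 response status are affected for longer, because they credit to ixekizumab responses first achieved on placebo or adalimumab. The sequence columns, the Combined Periods 2 and 3 analysis, and every primary and major secondary result are untouched.

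**What to change.** In Table RHBV.6.2, footnote c, restrict the pooled Total groups to safety and other non-efficacy tables. Report Period 3 efficacy, health-outcome and NSAID results by the sequence and IXE/IXE columns already listed. For health outcomes this is only for consistency, since Protocol Appendix 2 schedules none of those questionnaires at Week 20.

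If a pooled efficacy column is kept, add two rules:

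1. Exclude visits before a patient's first ixekizumab dose: Week 20 for ADA/IXE, and Week 16 for both ADA/IXE and PBO/IXE. The Week 20 efficacy assessment counts as before the dose given at that visit.
2. Do not pool the summaries by Week 16 response status.

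The cost is a footnote and output-shell edit, with no new data. The downside is either no pooled efficacy column or a smaller n at the early visits. At planned size and 1:1, n per regimen column would be 120 at Week 20 and 80 at Week 16, and 160 from Week 24 as before.
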